All data processing and analyses will be completed using custom R scripts (v.4.0.3). All postural sway data (i.e., center of pressure—COP) will be filtered through a 4th-order lowpass zero-lag Butterworth filter with a cut-off frequency of 6 Hz prior to analysis.

Recurrence Quantification Analysis (RQA)

RQA (Webber & Zbilut, 2005) will be used to assess the regularity of postural sway. RQA quantifies the patterning, non-stationarity, and complexity of biological time series through the analysis of local recurrences in a reconstructed phase space (Riley et al., 1999a). Recurrence plots (RPs) provide a visualization of patterns of recurrence, where a single point on the RP indicates a recurrence and a line indicates continuing recurrence (Coco & Dale, 2014). A variety of metrics are used to quantify these patterns. Percent determinism (%DET) is the percentage of recurrent points which fall on diagonal lines

and reflects how often the system repeats the same sequence of points. Thus, higher %DET is indicative of a system with more regularity. Maximum line length (MAXLINE) is the length of the longest diagonal line segment on the RP, indicating the maximum duration of time that the system is revisiting an area of reconstructed phase space. Mean line length (MEANLINE) is the average length of diagonal line segments on the RP, indicating the average duration of time that the system is revisiting an area of phase space. In the context of the current study, reduced task-sensitive adjustments (i.e., modulation in task relevant direction) in %DET, MAXLINE, and MEANLINE of postural sway (hypothesized to exist following constraining posture/task) would indicate a more regular postural control system—one that is prone to repeating the same behaviors. RQA metrics will be calculated separately for each plane.

Sample Entropy (SampEn)

SampEn (Richman, Lake, & Moorman, 2004) will be used to evaluate changes in the predictability of postural sway as a convergent measure to complement RQA. SampEn evaluates the predictability of the next state of a system, given what is known about the current state of a system (Yentes, 2016). SampEn has been widely used to assess the regularity of postural control across a variety of task conditions and populations (e.g., Schmit et al., 2016). SampEn will be calculated separately for each plane.

Traditional Analyses

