Due to the wide use of COP path length and standard deviation (SD) of COP in the literature, these metrics will also be measured to further quantify changes in postural sway. These metrics are also important for assessing the distribution of sway in each plane as a function of task demand. COP path length refers to the amount of displacement of the location of the (resultant) vertical ground reaction force vector. Increased COP path length is often interpreted as reduced stability. SD of the COP is the typical method used to quantify the variability in COP trajectories. Higher values for SD of the COP indicate increased variability. COP path length is a bi-planar measure whereas SD of the COP will be calculated separately for each plane.

Supra-Postural Task Performance

Root mean square (RMS) deviation of the observed supra-postural task performance from the expected values will be used to determine the accuracy of supra-postural task performance. For Experiments 1 and 2, this will be defined as the deviation of the laser position from the target. For the transfer task, this will be defined as the deviation from the target range of light touch force production.

Statistical Analysis

To characterize learning of the practiced supra-postural laser/target task and the associated postural sway patterns, trials (error score and postural sway metrics) for both experiments will be submitted to mixed-effects models. Group (experimental, control), test condition (pre-test, immediate post-test), limb (paretic, non-paretic), and their interactions will be entered as fixed effects, and participant will be entered as a random effect. To assess performance (error score and postural sway metrics) during the practice period, trial number (1-10), group (experimental, control), and their interaction will be

entered as fixed effects and participant will be a random effect. For the transfer task (error score and postural sway metrics), group (experimental, control), test condition (pre-test, immediate post-test), limb (paretic, non-paretic), and their interactions will be entered as fixed effects, and participant will be entered as a random effect. A backward stepwise approach will be used for model building. Simple effects and pairwise comparisons will be used to follow up on significant interactions.

Relevant References

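### Twenty-four pre/post models are planned with no primary outcome, alpha, testing order or multiplicity control; at an assumed 0.05, 1.2 false positives are expected on group x test, or 2.4 with group x test x limb

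*Combined protocol and SAP*

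**What the plan says.** The Statistical Analysis section of the combined protocol and SAP opens with its aim, "To characterize learning of the practiced supra-postural laser/target task and the associated postural sway patterns". It then says that "trials (error score and postural sway metrics) for both experiments will be submitted to mixed-effects models". The fixed effects are group, test condition, limb and their interactions, "and participant will be entered as a random effect". The transfer task gets the same treatment: "For the transfer task (error score and postural sway metrics), group (experimental, control), test condition" and limb are again entered with their interactions. A third set of models, with group and trial number, covers the practice period.

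The outcomes are defined in the preceding sections. RQA gives three metrics and SampEn one, each calculated per plane. Under Traditional Analyses, "COP path length is a bi-planar measure whereas SD of the COP will be calculated separately for each plane". Supra-Postural Task Performance gives one RMS error score per task.

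On selection and testing, the section says only this: "A backward stepwise approach will be used for model building". "Simple effects and pairwise comparisons will be used to follow up on significant interactions". No removal rule and no significance threshold is given. The one explicit hypothesis is in the RQA section and concerns reduced task-sensitive adjustments "in %DET, MAXLINE, and MEANLINE of postural sway (hypothesized to exist following constraining posture/task").

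The Participants section gives 10 participants per group, without a power calculation. The Practice section has participants with stroke practise with the paretic hand only.

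**The concern.** The study asks whether support during practice changes what is learned. That question is carried by the group-by-change terms (group x test and group x test x limb), and the plan tests them on many outcomes without ranking them.

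Suppose RMS error shows no group difference in change, but one of the 11 sway metrics does, in one plane, one task or one hand. The plan has no rule for whether that counts as evidence that support affects learning. The text does not supply one indirectly: the opening aim covers task learning and sway patterns in one sentence, while the explicit hypothesis is about the RQA metrics.

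Stepwise selection adds a second difficulty. The terms open to removal include those that answer the question. Because only the paretic hand is practised, an effect may be confined to that hand. If group x test x limb is removed, the group x test term that remains averages the two hands.

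**Working it through.** The document states no alpha, power or error rate, so there is no error-rate figure of its own to reproduce. Its one checkable count agrees: 2 hands x 2 test conditions x 2 trials = 8 test trials, as the Design section says.

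**Counting outcomes and models** (two planes assumed; the description of path length as bi-planar supports this)
- RMS error: 1
- %DET, MAXLINE, MEANLINE: 3 x 2 planes = 6
- SampEn: 2
- SD of COP: 2
- COP path length: 1
- Total: 1 + 6 + 2 + 2 + 1 = 12 outcomes, of which 11 are sway metrics
- Pre/post models: 12 x 2 tasks = 24

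The 12 practice models are left out because support acts directly on sway during practice. Experiment 2 is left out because it is not described.

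**Expected false positives** (no carry-over effect on any outcome, each test at an assumed two-sided 0.05)
- group x test: 24 x 0.05 = 1.2
- adding group x test x limb: 48 x 0.05 = 2.4

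These expected counts do not depend on how the outcomes are correlated.

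**Chance of at least one.** This does depend on correlation, which the document does not give. Under independence it is 1 - 0.95^24 = 71% and 1 - 0.95^48 = 91%. The other rows are simulated (10 v 10, two-sample t on 18 df, RMS error independent of sway, and the two contrasts independent of each other in the 48-test column).

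| Assumption | Sway correlation | 24 tests | 48 tests |
|---|---|---|---|
| All independent | 0 | 71% | 91% |
| Two tasks independent | 0.5 / 0.7 / 0.9 | 57 / 47 / 33% | 82 / 72 / 55% |
| Sway equally correlated across both tasks | 0.5 / 0.7 / 0.9 | 51 / 38 / 25% | 76 / 62 / 43% |

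The last row deserves weight, because the same 20 people stand on the platform in both tasks.

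**Averaging over hands.** Let the effect be δ in the paretic hand and 0 in the other. With group x test x limb removed, group x test estimates (δ + 0)/2 = δ/2.

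**Power of the two terms.** Take δ as the size a paretic-only test detects with 80% power: d = 1.325 in per-hand change SDs (noncentral t, 18 df). Let c be the correlation of change between hands, assumed 0 / 0.3 / 0.5.
- Three-way term: d = 1.325/√(2(1 - c)) = 0.94 / 1.12 / 1.325, non-significant in 49 / 34 / 20% of trials.
- group x test: d = 1.325/√(2(1 + c)) = 0.94 / 0.82 / 0.76, power about 51 / 41 / 37%.

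**The case against.** The strongest reply is that this is a 20-participant laboratory study whose stated aims are to characterise learning and assess performance, so formal error control may be out of proportion. That has force, and it is why an exploratory declaration is one acceptable remedy. But the plan does not make that declaration, and it relies on significance to trigger follow-up tests without defining it.

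The plan also gives the sway measures somewhat different roles: SampEn is introduced as a convergent measure alongside RQA, and path length and SD as further description. This is fair, but it does not amount to a hierarchy, and it does not rank RMS error against RQA.

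Three stronger readings are tempting and are not supported.
- A reader might infer that a false positive is more likely than not. Over 24 tests that holds at low correlations only; with sway highly correlated and shared across tasks the chance is 25%.
- A reader might take the 49 / 34 / 20% as harm done by stepwise selection. It is the type II error of the three-way test, and a full model with no selection would find the term non-significant equally often. It reflects low power with 10 per group. Nor is the averaged term worthless: its estimate is halved, but its standard error also shrinks, and it keeps the power shown above. Selection matters because it can leave a model that no longer contains the contrast of interest, under a rule nobody has stated.
- A reader might infer that the document makes RMS error primary because laser-task learning is mentioned first. The same sentence covers the associated sway patterns, so RMS error can only be a proposal.

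**Conclusion.** The concern holds. The plan has 24 pre/post models and no primary outcome or contrast, alpha, testing order, multiplicity control or exploratory label. The count rests on two planes and the three named RQA metrics. The expected 1.2 (24 tests) or 2.4 (48 tests) false positives rest on an assumed two-sided 0.05, no true carry-over effect, and each test holding its nominal size. That last assumption is open, since neither the form of the participant random effect nor the stepwise rule is specified. The chance of at least one false positive cannot be fixed from the document. In the scenarios examined it is 25% to 71% for 24 tests and 43% to 91% for 48, at least five times the nominal 5%.

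Stepwise selection compounds the gap, because the group-by-change terms are not protected from removal and loss of the three-way term halves the estimate of a paretic-only effect. No percentage cost of selection is claimed.

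**What to change.** Before outcome data are seen, amend the SAP as follows.

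1. State alpha (for example 0.05 two-sided) and name one primary contrast, fitted without stepwise selection. Proposed: paretic-hand laser RMS error, as the post-test group difference adjusted for the participant's pre-test mean. If the RQA hypothesis is the main question, name one RQA metric in one plane instead.
2. Test the same contrast on transfer-task RMS error second, only if the primary is significant.
3. Treat the sway metrics as secondary, with one such contrast per metric and Holm within each task. Label these two families supportive and outside study-wide error control.
4. Keep the planned 2 x 2 x 2 models, without selection on the group-by-change terms, together with the practice models and pairwise follow-ups, as exploratory.
5. If no confirmatory claim is intended, say so and report estimates with confidence intervals.

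This needs no new participants or measurements. The cost is fewer sway results called significant. If all 11 sway metrics in a task form the Holm family, the first step is 0.05/11 = 0.0045. With 10 per group (noncentral t, 18 df), the effect detectable with 80% power then rises from d = 1.32 to 1.86, in SDs of the analysed score, and power at 1.32 falls from 80% to 42%. The primary keeps full alpha.

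Baseline adjustment is a proposal with a modest gain. In post-test SDs, with equal pre and post SDs and allowing for chance baseline imbalance, it detects about 1.31 / 1.19 / 0.98 with 80% power at assumed pre/post correlations of 0.3 / 0.5 / 0.7. For change scores the values are 1.325 x √(2(1 - r)) = 1.57 / 1.32 / 1.03. Naming the contrast matters more than choosing between the two.

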In Experiment 1, participants will be required to learn an upper limb precision aiming task while receiving postural support (i.e., balance facilitation) or no postural support. Baseline performance will be measured prior to a practice period. For this pre-test, participants will stand on the force platform for 30 s trials. Within the VR environment, participants will see an anteriorly placed circular target and will be instructed to maintain the position of a virtual laser pointer in the target via a handheld device in the dominant hand (or both the non-paretic and paretic hands for participants with stroke) with the upper limb held at the side. The target will change color to communicate task accuracy to participants: When the virtual laser is correctly positioned within the target, the target will be blue, but misaiming will turn the target red, indicating the need to correct the laser position. Participants will only visualize the laser and target in VR; there will not be a virtual representation of the upper limb. Participants with stroke will complete two 30 s pre-test trials with each hand (paretic and non-paretic). Postural sway and projection of the laser will be measured and recorded.

Transfer Task

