As therapists expect that training in a set of tasks might benefit performance of other similar but untrained tasks (i.e., transfer), a task to assess transfer will also be implemented. This task will be completed both prior to the practice period (to obtain a baseline level of performance for comparison after practice) and after the practice period. In the transfer task, participants will attempt to use their dominant hand (or both non-paretic hand and paretic hand for participants with stroke) second digit to produce a specified level of light touch force (0.5-1 N to prevent physical stabilization) on the force transducer. Like the laser pointer task, this task requires integration of postural control with precision manual performance (e.g., Riley et al., 1999b). Participants will receive visual feedback regarding their level of light touch force production on a visual display. A vertical bar will appear on the screen. The bar will increase in vertical size with increased force production and decrease in size with less force production. The bar will change color to reflect the level of force production. When the bar is blue, the desired level of force production has been achieved. When the bar is red, the participant needs to alter the level of force production. A horizontal line will also indicate target force production. Participants will complete two 30 s trials of the transfer task. Participants with stroke will complete the transfer trials with each limb.

Practice

Following the pre-test and baseline transfer task, participants will engage in 10, 1 min practice blocks in which they are to practice the laser task with the target positioned

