laterally. This lateral placement of the target during the practice period (as opposed to the anterior position of the pre-test) will prevent one group of participants from practicing under the exact conditions of the pre-test, which could bias the results. This will also allow for an assessment of differences in sway variability that may facilitate performance at post-test, thus providing insights about generalizability. The control group will receive no physical support to maintain balance. The experimental group will receive physical support (whether physical support is warranted or not) to minimize postural sway fluctuations. Participants with stroke will use the paretic hand. Participants will be outfitted with a gait belt, and physical support will be provided through the use of the gait belt and other traditional physical therapy guarding techniques (O'Sullivan et al., 2019). Thus, participants in this group will not be required to coordinate posture and task performance because postural stabilization will be provided externally through physical support. Postural sway and virtual laser position will be synchronously recorded during the practice period. Participants will rest for a self-selected period between each trial.

Immediate Post-Test and Retention

Participants will complete a post-test following the same procedure as the pre-test (i.e., target task). The post-test will also involve the previously described transfer task. Participants will complete two 30 s trials of each task (target/force production). Participants with stroke will complete the trials with each limb. Task and condition will be randomized. No physical support will be provided in the post-test.

Design

To evaluate the learning effect in participants with stroke, the two groups (experimental, control), two hands (paretic, non-paretic), and two test conditions (pre-test, immediate post-test) will result in a $2 \times 2 \times 2$ mixed design for Experiment 1. Participants with stroke will complete 2 trials of each test condition per limb for a total of 8 test trials per participant. To evaluate the role of therapist support during practice, each participant will complete 10 practice trials. Participants will complete 4 trials (2 trials per limb) of the transfer task before and after practice for a total of 8 trials.

Proposed Data Analysis

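### Group is left free at the pre-test and no group contrast is protected from stepwise removal; a pre-specified, baseline-adjusted group difference for each hand would be a cheap improvement, not an error fix

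*Combined protocol and SAP*

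**What the plan says.** The Statistical Analysis section submits the target-task trials to a mixed-effects model in which "Group (experimental, control), test condition (pre-test, immediate post-test), limb (paretic, non-paretic), and their interactions will be entered as fixed effects", with participant as the random effect. The transfer task repeats the structure: "For the transfer task (error score and postural sway metrics), group (experimental, control), test condition (pre-test, immediate post-test), limb (paretic, non-paretic" and their interactions. Neither model has a baseline covariate or sets the groups equal at the pre-test.

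The same section adds that "A backward stepwise approach will be used for model building" and that "Simple effects and pairwise comparisons will be used to follow up on significant interactions". No term is named as exempt from removal.

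The data for an adjustment are already planned. Under Pre-Test, "Baseline performance will be measured prior to a practice period" and "Participants with stroke will complete two 30 s pre-test trials with each hand (paretic and non-paretic". Under Transfer Task, the pre-practice trials are run "to obtain a baseline level of performance for comparison after practice". Under Design, "Participants with stroke will complete 2 trials of each test condition per limb for a total of 8 test trials per participant". The Participants section assigns 10 people to each group at random, and the Practice section has participants with stroke practise with the paretic hand.

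**The concern.** Two features of the plan act on the same quantity, the randomised comparison of groups after practice.

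- **Weight given to the pre-test.** Because group is free at both tests, the group-by-test contrast subtracts the whole observed pre-test difference. Under randomisation the expected difference is zero, so what is subtracted is noise to the extent that the pre-test does not predict the post-test. With 10 people per group that noise may matter. ANCOVA estimates the weight from the data instead of fixing it at 1.
- **Survival of the contrast.** If the three-way term is eliminated, the hand-specific group contrast disappears. If group-by-test is eliminated too, the model gives no estimate or interval for the effect of support on learning. Since only the paretic hand is practised, the effect could differ by hand, and with 20 participants a non-significant interaction is weak evidence that it does not.

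At stake are some precision and the assurance that the group comparison is reported whatever the selection procedure does.

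**Working it through.** **Inputs.** From the documents: n = 10 per group (N = 20), and 2 trials per hand per test. Assumed, because the documents give neither: single-trial correlation r = 0.3 to 0.7 (the same within and between sessions), and k = post-test SD / pre-test SD.

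**Design count.** 2 tests × 2 hands × 2 trials = 8 test trials per participant, as the Design section states; 20 × 8 = 160 trials. The documents give no power calculation to reproduce.

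**What the planned contrast is.** The planned model was fitted to one simulated balanced data set. With the three-way term in, its group-by-test estimate for the reference hand was -0.4806, equal to the between-group difference in mean change for that hand. With the three-way term out, it was -0.3602, equal to the difference in change averaged over hands.

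**Variance of the estimate, one hand.** With ρ the correlation of the pre- and post-test 2-trial means and s the SD of the pre-test mean:

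- ρ = 2r/(1 + r), which is 0.46, 0.67 and 0.82 at r = 0.3, 0.5 and 0.7.
- Var(change) = (2/n)·s²·(1 + k² − 2ρk).
- Var(ANCOVA) = (2/n)·s²·k²·(1 − ρ²)·[1 + 1/(N − 4)]. The last factor is 17/16 at N = 20, for a roughly normal pre-test.

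At k = 1 the ratio reduces to (17/16)(1 + ρ)/2. For r = 0.3 this is 1.0625 × 0.7308 = 0.776.

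| k | r = 0.3 | r = 0.5 | r = 0.7 |
|---|---|---|---|
| 0.8 | 0.594 | 0.659 | 0.679 |
| 1 | 0.776 | 0.885 | 0.969 |
| 1.25 | 0.927 | 1.030 | 1.061 |
| 1.5 | 1.009 | 1.062 | 0.987 |

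Simulation agreed closely with the formula.

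**Ceiling.** Since 1 + k² − 2ρk = k²(1 − ρ²) + (1 − kρ)², the ratio cannot exceed 17/16 = 1.0625, reached when kρ = 1. With 16 completers the factor is 1 + 1/12 = 1.083. At k = 1 the gain is gone once ρ reaches 2/1.0625 − 1 = 0.88.

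**Hand-averaged contrast.** For 4-trial means, ρ = 4r/(1 + 3r). The ratios at k = 1 are 0.867, 0.956 and 1.011, that is 13% lower to 1% higher.

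**Interval against the planned model.** The planned model pools residuals over hands and tests: 160 trials − 20 participants − 6 within-participant fixed effects = 134 df. Each ANCOVA has 20 − 3 = 17. Simulated with no true effect, equal SDs and only a participant effect, the ratio of ANCOVA to planned CI width was 0.93, 0.99 and 1.04 at r = 0.3, 0.5 and 0.7.

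**If that covariance is wrong.** With variances of 0.5 (participant), 0.2 (participant-by-limb) and 0.3 (residual), the planned per-hand test rejected about 2% of the time at a nominal 5%. With 0.2 placed on participant-by-test instead, it rejected about 13%. ANCOVA stayed at about 5% in both.

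**The case against.** The strongest reply is that a factorial mixed model of randomised pre/post data is a valid analysis and the alternative is only a preference. That stands. A reader might infer that the planned contrast is biased by baseline imbalance. The documents do not support this: allocation is random and the pre-test comes before any support is given, so both estimators target the same effect without bias.

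A reader might also infer that ANCOVA always gains. It does not. The sign depends on correlations and SDs that the documents do not give. If practice widens the spread of scores, the variance can be slightly higher. Against the planned pooled interval there is practically no gain at r = 0.5 and a small loss at r = 0.7. This stands as a limit, but the planned interval's advantage holds only if the participant-only covariance is right.

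The documents name no primary contrast, so the per-hand difference cannot be called the trial's declared target. If a hand-averaged effect is wanted, the smaller range applies.

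Multiplicity is a fair point too. Three recurrence metrics, sample entropy and SD in two planes give 10 outcomes; path length and error make 12. Over two tasks and two hands that is 12 × 2 × 2 = 48 contrasts, too many to treat as confirmatory tests.

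Finally, the stepwise point is separate from the choice of estimator. That is correct. It does not argue for ANCOVA, but whichever estimator is used, the contrast needs protection from removal.

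**Conclusion.** The concern holds as an optional improvement. On variance, the adjusted per-hand estimate is 22% to 3% lower than the change score over r = 0.3 to 0.7 if pre- and post-test SDs are equal. It is at worst about 6% higher with 20 completers, or 8% with 16, given a roughly normal pre-test. On interval width against the planned model, the result runs from 7% narrower to 4% wider if SDs are equal and the participant-only covariance is exactly right. If that covariance is wrong, the planned interval can be too wide or too narrow, while ANCOVA keeps about 5% error.

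The case for pre-specifying the contrast and exempting it from elimination does not depend on any of these assumptions. It follows from the stepwise and follow-up rules as written. Those rules allow the contrast to be lost; they do not show that it will be.

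**What to change.** For each target-task and transfer-task outcome, pre-specify the post-test group difference for each hand, from an ANCOVA of the post-test 2-trial mean on the same-hand pre-test 2-trial mean plus group. Report it with a 95% CI and state that it is not subject to backward elimination. Present these contrasts as estimates with intervals, not as confirmatory tests. Keep the planned mixed model for within-group learning.

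A model with a common pre-test mean is an equivalent choice only if pre- and post-test variances may differ. With random intercepts alone it forces them equal and can lose precision.

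The cost is a few sentences in the SAP and one simple model per hand and outcome, with no new data. The price in precision is the drop from about 134 to 17 df, and a possibly higher variance within the ceiling given above.

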**The Motor Control Consequences of Excessive Physical Therapist Support in
Individuals with Stroke (NCT04856527)**

University of Cincinnati IRB Protocol 2020-1072

Most recent IRB approval: 2021-10-07

STUDY PROTOCOL AND STATISTICAL ANALYSIS PLAN

Study Protocol

Participants

Twenty participants aged 21-85 years¹ previously diagnosed with stroke (>1-month prior to enrollment to ensure medical neurologic stability) will participate in Experiment 1 (10 participants in experimental group, 10 participants in control group). Participants will be randomly assigned to a group. Participants must demonstrate independence or modified independence during ambulation (defined as the ability to ambulate with no physical assistance and use an assistive device as needed). Participants must score 0-3 on the Modified Rankin Scale (de Haan et al., 1995; Rankin, 1957), which indicates complete independence to moderate disability but able to walk without assistance. Participants must be able to maintain standing balance for >2 minutes with no physical support and maintain grasp of a handheld object with at least one hand. Participants are permitted to be active in programs of physical therapy or occupational therapy at the time of enrollment. All gender identities and all races/ethnicities will be eligible for participation.

Participants with stroke will be excluded due to limited language/cognitive abilities, deafness, blindness, or serious motor impairment that outright prevents performance of the experimental tasks (e.g., severe upper or lower extremity spasticity). Participants will be excluded if they are pregnant. Participants will also be excluded if they experience pain with weightbearing >4/10. Participants will complete the Mini Mental State Exam (Folstein et al., 1975) prior to study start to ensure cognitive capacity to engage in and consent to the study. Participants will be excluded if they have any other medical condition that would preclude the valid administration of the study measures, specifically seizure disorders, additional neurologic conditions beyond stroke, or significant musculoskeletal conditions (e.g., lower limb amputation).

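### With participant as the only random effect, all three group interactions in the learning and transfer models are tested against one pooled 134-df trial-level residual instead of participant-level error on 18 df

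*Combined protocol and SAP*

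**What the plan says.** The Statistical Analysis section states that "trials (error score and postural sway metrics) for both experiments will be submitted to mixed-effects models". For learning, group, test condition, limb "and their interactions will be entered as fixed effects, and participant will be entered as a random effect". The transfer model repeats these terms. For practice the terms are "trial number (1-10), group (experimental, control), and their interaction will be" "entered as fixed effects and participant will be a random effect". The section adds: "A backward stepwise approach will be used for model building". It then says: "Simple effects and pairwise comparisons will be used to follow up on significant interactions". It names no random slope, no participant-by-test or participant-by-limb term, no covariance structure and no method for denominator degrees of freedom.

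The Participants section randomises 20 people, 10 to each group. The Design section gives each participant 8 trials per task: two per limb, before and after practice.

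**The concern.** Group is assigned to participants, so whether it alters change, limb gap or change in limb gap has to be judged against how much participants in the same group differ on that quantity. A random intercept removes only differences in overall level. Differences between participants in response go into the same residual as trial noise, and that one residual serves all three group interactions.

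Group x test asks whether support during practice changes learning. The three-way term asks whether that differs between the practised and unpractised hand. These are the study's questions. The same residual also decides which terms survive backward elimination and sets the standard errors of the follow-up comparisons, for the error score and for every sway metric. The error can go in either direction, so a reader could not correct for it by discounting p-values.

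**Working it through.** **Inputs from the documents.** 2 groups of 10; 2 tests; 2 limbs; 2 trials per cell. Trials per participant: 2 x 2 x 2 = 8, as the Design section states.

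**Assumptions.** Trial SD is set to 1. Let c, l and d be the SDs between participants of pre-post change, limb gap and change in limb gap. The documents give none of these, so a range is shown. Alpha is taken as 5%, with complete data and the full model.

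**Degrees of freedom.** Rows: 20 x 8 = 160. Residual df: 160 - 20 - 6 = 134. These are 18 for participant x test, 18 for participant x limb, 18 for participant x test x limb, and 80 for trial noise within cells.

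**Expected mean squares.**
- Correct error for group x test: 1 + 2c²
- Correct error for group x limb: 1 + 2l²
- Correct error for the three-way term: 1 + d²/2
- Pooled residual used by the plan: 1 + (36c² + 36l² + 9d²)/134

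**Result that needs no assumed SD.** Write S = c² + l² + d²/4. The pooled residual exceeds 1 by 2 x (18/134) x S, that is 2 x 0.134 x S. The largest of the three components is at least S/3, so its correct error exceeds 1 by at least 2 x 0.333 x S. If any SD is above zero, at least one group interaction is therefore tested against too small an error. A term with less than 13.4% of S is tested conservatively. All three tests are correct only when c = l = d = 0.

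**Example, (c, l, d) = (1, 0, 0).** Correct error for group x test: 1 + 2 = 3. Pooled residual: 1 + 36/134 = 1.27. Ratio: 2.36. The standard error of the group difference in change should be √[(1 + 0.5) x 2/10] = 0.548. The plan gives √[0.5 x 1.27 x 2/10] = 0.356.

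**Actual error at nominal 5%**, from 400,000 to 1,000,000 draws of the exact chi-square form:

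| (c, l, d) | Group x test | Group x limb | Three-way |
|---|---|---|---|
| (0, 0, 0) | 5.0% | 5.0% | 5.0% |
| (0.1, 0.1, 0.1) | 5.1% | 5.1% | 5.0% |
| (0.25, 0.25, 0.25) | 5.9% | 5.9% | 4.9% |
| (0.5, 0.5, 1) | 7.9% | 8.0% | 7.9% |
| (0.5, 1, 1) | 5.9% | 17.9% | 5.8% |
| (1, 0, 0) | 20.1% | 2.8% | 2.8% |
| (0, 0, 2) | 2.8% | 2.8% | 20.1% |
| (0, 2, 0) | 0.6% | 34.6% | 0.6% |
| (0, 2, 2) | 0.4% | 31.8% | 8.5% |
| (1, 1, 1) | 15.1% | 15.1% | 4.4% |
| (1, 1, 2) | 12.8% | 12.8% | 12.8% |

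Direct simulation of data (20,000 sets in each of 16 scenarios) agreed within about 0.4 points. Participant-level contrasts on 18 df held 4.7% to 5.3% in every simulation.

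**Break-even for group x test.** Setting 2c² equal to the pooled excess gives l² = (232/36)c² - d²/4 = 6.44c² - d²/4. Being at nominal there does not rescue the other terms: with c = 0.25 and d = 0, group x limb is at 12.1% and the three-way term at 3.8%.

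**Practice model.** Let T be the SD between participants of total change over trials 1 to 10. If trial number is numeric, the correct error for group x trial is 1 + 82.5(T/9)², while the plan uses a pooled residual on 200 - 20 - 2 = 178 df. For T = 0.5, 1 and 2 the actual error is 7.6%, 14.7% and 30.1%. If trial number is a factor (9 and 162 df) it is 5.1%, 5.6% and 8.5%.

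**The case against.** The strongest case on the other side has four parts.

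- **The text does not say intercept only.** True, but it names no slope, and backward elimination cannot add one that was never entered. If slopes are intended, writing them down costs nothing.
- **The documents do not show that c, l or d is above zero.** Fair in part. The Rankin range ("Participants must score 0-3 on the Modified Rankin Scale") mainly shows differences in level, which the intercept absorbs. Practice with one hand ("Participants with stroke will use the paretic hand") creates a mean difference, which the fixed effects cover. Neither proves that participants respond differently. But the planned tests need every participant to share exactly the same change and the same limb gap, and that is hard to assume in this population.
- **The guaranteed inflation may fall on group x limb, which is not a learning effect.** This stands. If limb gap varies most, the two learning terms can lie near nominal, as at (0.5, 1, 1). The 20% figures come from corners where the SD of limb gap is zero. Yet (1, 1, 1) gives 15.1% for group x test, and (1, 1, 2) gives 12.8% for all three terms.
- **134 df is conditional.** It holds for the full model with complete data; dropping fixed terms raises it to at most 140. The transfer sentence does not repeat that trials are entered singly. Averaging the two trials would leave a pooled 54-df residual and the same fault.

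**Conclusion.** The concern holds. Read in the ordinary way, the plan tests all three group interactions in the learning and transfer models on the wrong error term, and at least one is too liberal as soon as participants differ in any of the three responses. That conclusion rests only on the design and the random-intercept reading.

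The size rests on assumed SDs. For c from 0 to 1 and l and d from 0 to 2, actual error runs over 0.4% to 20.1% for group x test, 1.6% to 34.6% for group x limb, and 0.4% to 20.1% for the three-way term. If all three SDs are small, the effect is small. Which term suffers cannot be settled from the documents. The practice model has the same gap, serious mainly if trial number is numeric. The group main effect is not affected.

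This must be fixed before analysis, because the terms that carry the study question have no dependable error rate and the remedy is valid whatever the SDs are.

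**What to change.** 1. **Learning and transfer, main analysis.** Average the two trials in each cell. For each participant compute change, limb gap and change in limb gap, and compare each between groups on 18 df. Use participant-level contrasts for the follow-up comparisons too.
2. **Acceptable alternative.** Fit a mixed model with a participant intercept and uncorrelated, sum-coded by-participant slopes for test, limb and their product, with Kenward-Roger or Satterthwaite df. In 15 scenarios this gave 3.8% to 5.1% for all three terms. At least one variance was estimated at zero in 1% to 86% of data sets, so name option 1 as the fallback for a singular fit. Do not replace the product slope with a plain participant-by-test-by-limb cell intercept: that gave up to 14.4% for the three-way term.
3. **Practice.** State whether trial number is numeric or a factor. If numeric, compare participant slopes on 18 df or add a by-participant slope.
4. **Model building.** State that backward elimination does not remove these random terms.

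The cost is SAP wording and a little R code; no new data are needed. Critical t rises from 1.98 to 2.10. If all three SDs really are zero, a contrast with 80% power under the plan has 76%. Otherwise standard errors widen where they were too small and narrow where they were too large.
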